## **3.4 Blinding**

Because of different volumes for RIG and SYN023 this study is incompletely blinded. In a strict sense it is a single blind study since the subject will not be told which treatment he or she is receiving. The sponsor and the medical monitor are unblinded. The statistician is unblinded.

The other unblinded persons on the study are the study drug manager or pharmacist (and designee, if appointed) and the study monitor(s). All unblinded persons must take care to not reveal individual subject treatment regimen assignments to any other member of the study team. The subject, the principal investigator and most of the study team remain blinded to reduce bias in safety assessment.

The study drug manager or pharmacist (and designee) must have no other clinical or regulatory responsibilities associated with the conduct of the study during the entire study period. With the exception of the medical monitor, unblinded study personnel must not participate in the evaluation of adverse events. A Delegation of Authority Log will be maintained by the site and will identify the individual(s) authorized to function as the study drug manager, i.e., individuals with access to study blinding information.

The randomization schedule will be provided by the unblinded statistician to the study drug manager in a sealed tamper-evident envelope. Access to the randomization schedule during the study will be provided only to the study drug manager (or designee in the pharmacy), the study monitor, and the sponsor's investigational product manager (and/or designee). The randomization schedule and all pharmacy source documents and dose preparation records that can link a subject identification number with a treatment assignment must remain secure (e.g., in the pharmacy with access limited to only unblinded persons) until notification from the sponsor that the study has been unblinded.

Labels accompanying the syringes of prepared study drug doses will not indicate which vaccine is in the syringe. Identical syringes and needles will be used for preparation and administration of each study drug.

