## **3.3 Study Randomization and Sentinel Subjects**

Subjects will be randomized to the study based on a randomly-generated sequence of subject identification numbers (randomization schedule). The randomization schedule will be prepared by a statistician who will not be involved in the analysis of the study in order to maintain the blind of the study team. A subject is considered randomized when a subject identification number has been assigned to them on Study Day 0. The first four subjects entered into the study (sentinel subjects) will be randomized such that a subject each receives one of the four possible regimens. Safety information on these sentinel subjects through study day 14 will be collected and reviewed by the medical monitor and principal investigator before the remainder of the trial is enrolled.

Subjects who withdraw from the study or are discontinued may be replaced by modification of the remaining randomization schedule. Unless there is reason to pause the study, based on the study pausing rules as outlined in Section 6.1, then the principal investigators may proceed to enroll all of the subjects.

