#### **5.1.4 Safety Monitoring Committee**

If study drug administration is paused (see safety pausing rules in Section 6.1) by the principal investigator, the local medical monitor, or the global medical monitor, an SMC will be convened. The SMC composition is described in an SMC charter. The voting members cannot be directly involved with the conduct of the study. Voting members cannot be employees of the sponsor. Additional subject area experts may be present to provide expertise if requested by the SMC. The SMC may review an individual SAE or it may choose to review adverse events, serious

adverse events, solicited adverse events, and laboratory and vital signs data. The SMC may unblind any amount of safety information needed to conduct their assessment. Only the SMC and the independent statistician responsible for preparing these analyses would be unblinded during these reviews. All procedures associated with this review, including objectives, data handling, and elements to be included for review will be documented in SMC minutes.

Based on its review and the protocol stopping rules (Section 6) the SMC will make recommendations in the SMC minutes to the sponsor regarding further conduct of the study and further administration of study drug. The conclusions of the SMC will be communicated to the investigators and the Institutional Review Boards/Ethics Committees and the national regulatory authority. The sponsor agrees to abide by the decision of its SMC and any directives issued by the national regulatory authority, the Institutional Review Board or Ethics Committee.

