PTT	Partial thromboplastin time
QI	Qualified Investigator
RVNA	Rabies virus neutralizing activity
RIG	Rabies immune globulin
RVa	RabAvert®
RVi	Imovax®
SAE	Serious adverse event
SAP	Statistical analysis plan
SAS	Statistical Analysis System
SD	Standard Deviation
SOC	System organ class
SOP	Standard operating procedure
T_{max}	Time of maximal observed plasma concentration
T_{max,E}	Time of maximum observed effect
T_{1/2 el}	Terminal elimination half-life
VR	Ventricular Rate
WHO DDE	World Health Organization Drug Dictionary Enhanced

1. Introduction

This statistical analysis plan (SAP) is intended to give a detailed description of the summaries and the analyses that will be generated for the present study by inVentiv. Analyses specified in this plan are based on Synermore Biologics Co., Ltd study protocol No. SYN023-002, dated June 21, 2016 (inVentiv Project No. 162009). Safety, tolerability, pharmacokinetic (PK) and Pharmacodynamic (PD) analyses will all be described.

The plan may change due to unforeseen circumstances and any changes made after the plan has been finalized will be documented. If additional analyses are required to supplement the planned analyses described in the SAP, the changes and justification for the changes will be outlined in the clinical study report (CSR). No change will be made without prior approval of the study sponsor. No revision to the SAP is required for changes that do not affect the statistical analysis methods, definitions, or rules defined in this document.

When applicable, all methodology and related processes will be conducted according to inVentiv's Standard Operating Procedures (SOPs). Protocol deviations occurring during the study will be listed.

2. Study Objectives

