6.2 Per-Protocol Population

The PP population will consist of all randomized subjects who received all scheduled doses of a study treatment and remained on study for at least 28 days without major protocol violation. Treatment allocation will be based on as treated principle.

7. Interim Analyses

A review of Rabies Virus Inhibitory Activity, anti-SYN023 antibodies, SYN023 PK information and clinical safety data will be conducted following completion of Study Day 42. This review may present individual and aggregate (mean, median or 95% CI, as appropriate) and change from pre-study drug to each post administration time point by individual or in aggregate. Study procedures and monitoring practices will not change following this preliminary review. No decision cut points or stopping rules will be stipulated. No hypothesis testing will be performed. The purpose of this review is to obtain preliminary data for use in the decision-making process regarding Study Drug dose level. Personnel at the research site and at the immunology laboratory will remain blinded to all study results and to treatment assignments until after the Study Day 112 data have been collected, reviewed and queries resolved.

8. Study Population and Exposure

Shells for all summary descriptive statistic tables and listings referred to in this section are displayed in a separate document; the shells may be revised as they are presented to illustrate the general layout of data to be included in the final report.

No inferential analyses will be done.

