10.3 Efficacy/Pharmacodynamic Parameters

A total of 10 blood samples will be drawn from each subject for efficacy/PD analyses. Blood samples will be collected on Day 0, Day 1, Day 3, Day 7, Day 14, Day 28, Day 35, Day 42, Day 84, and Day 112.

RVNA will be used to calculate the following parameters by standard non-compartmental methods:

AUEC_{0-t}: area under the effect-time curve above the minimum rabies virus neutralizing activity threshold (0.5 IU/mL) from time 0 to the last measurable concentration, calculated using the linear trapezoidal method. Unit will be Day*IU/mL.

AUEC₀₋₇: area under the effect-time curve above the minimum rabies virus neutralizing activity threshold (0.5 IU/mL) from time 0 to 7 days, calculated using the linear trapezoidal method. In case where the 7 days RVNA value is missing, AUEC₀₋₇ will be interpolated at the discretion of the pharmacokineticist. Unit will be Day*IU/mL.

- AUEC₀₋₁₄: area under the effect-time curve above the minimum rabies virus neutralizing activity threshold (0.5 IU/mL) from time 0 to 14 days, calculated using the linear trapezoidal method. In case where the 14 days RVNA value is missing, AUEC₀₋₁₄ will be interpolated at the discretion of the pharmacokineticist. Unit will be Day*IU/mL.
- AUEC_{14-t}: area under the effect-time curve above the minimum rabies virus neutralizing activity threshold (0.5 IU/mL) from time 14 days to the last measurable concentration, calculated using the linear trapezoidal method. In case where the 14 days RVNA value is missing, AUEC_{14-t} will be interpolated at the discretion of the pharmacokineticist. Unit will be Day*IU/mL.
- AUEC₁₄₋₃₅: area under the effect-time curve above the minimum rabies virus neutralizing activity threshold (0.5 IU/mL) from time 14 days to 35 days, calculated using the linear trapezoidal method. In case where the 14 days or 35 days RVNA value is missing, AUEC₁₄₋₃₅ will be interpolated at the discretion of the pharmacokineticist. Unit will be Day*IU/mL.
- E_{max}: maximum observed effect. Unit will be IU/mL.
- T_{max,E}: time of observed E_{max}. Unit will be Day.

Some efficacy/PD parameters may not be calculated for all or some subjects, at the discretion of the inVentiv pharmacokineticist, if the concentration data is not deemed to be amenable to evaluation. Explanations for efficacy/PD parameters that could not be estimated will be provided in the CSR.

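### Neither document requires per-protocol membership or omission of a subject's AUEC0-t to be decided blind to arm, while Protocol 3.4 unblinds the sponsor and an unspecified statistician

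*Protocol*

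**What the plan says.** **Who is unblinded.** Protocol 3.4 calls the trial incompletely blinded because RIG and SYN023 differ in volume, and then says: "The sponsor and the medical monitor are unblinded. The statistician is unblinded". Protocol 3.3 has the randomization schedule "prepared by a statistician who will not be involved in the analysis of the study in order to maintain the blind" of the study team. Later in 3.4: "The randomization schedule will be provided by the unblinded statistician to the study drug manager". During the study, 3.4 limits schedule access to the study drug manager, the study monitor and the sponsor's product manager, or designees. For safety committee reviews, Protocol 5.1.4 adds: "Only the SMC and the independent statistician responsible for preparing these analyses would be unblinded during these reviews".

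**Who is blinded.** The subject, the principal investigator and most of the study team (Protocol 3.4). Site and immunology laboratory staff stay blind until the Day 112 data are collected, reviewed and cleared of queries (Protocol 7.8.1, SAP 7).

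**What is decided, and by whom.**
- SAP 10.4.1 applies the 80.00-125.00% rule to AUEC0-t in the per-protocol population.
- SAP 6.2 requires that subjects received all scheduled doses and "remained on study for at least 28 days without major protocol violation".
- SAP 10.3: "Some efficacy/PD parameters may not be calculated for all or some subjects, at the discretion of the inVentiv pharmacokineticist". The condition is that the data are judged unfit for evaluation, and the reason must appear in the study report.
- The sponsor may withdraw subjects, as may the investigator (SAP 3.4), and may replace those who do not reach Day 28 (Protocol 3.6.7). On the analysis plan, SAP 1 says: "No change will be made without prior approval of the study sponsor".

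**The concern.** A per-protocol equivalence-type comparison is only as sound as the process that decides who is in it. Here two decisions act directly on the AUEC0-t ratio: whether a deviation counts as major, and whether a subject's area is calculated. Both call for judgement. If someone who knows the arm makes them, even in good faith, a few low responders in one arm may be judged differently from those in the other, and the estimated ratio moves toward 1. At stake is a false conclusion that vaccine response with SYN023 is similar to that with RIG, which is the primary objective.

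**Working it through.** No figure in the plan bears on blinding, so the check sets the sections side by side and then bounds the possible effect.

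**1. Which statistician?** Protocol 3.3 keeps the schedule statistician out of the analysis. Protocol 3.4 uses the term unblinded statistician for the person who hands over the schedule. Read together, these most naturally mean one person. But the general sentence in 3.4 carries no such limit, and neither document states whether the analysis statistician is blind.

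**2. Is the pharmacokineticist blind?** Not stated. SAP 12.3 computes PK parameters only for Treatments C and D, so whoever does that work knows those subjects received SYN023. Neither document separates the PK work from the PD work.

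**3. Is a major violation defined?** Protocol 7.2 leaves protocol deviations to be defined in the SAP. SAP 8.2 only lists them by case report form category. SAP 6.2 gives no definition, no decision maker and no timing.

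**4. Would selective exclusion show?** Protocol 7.1 defines an intent-to-treat efficacy population of all randomized subjects who received at least one dose. SAP 6 keeps only the safety and per-protocol sets, and SAP 10 runs all PD analyses on per-protocol.

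**5. How large could the effect be?** Inputs:
- 80 subjects per antibody group (two vaccine arms of 40, SAP Table 10-1, with the interaction term dropped).
- True RIG/SYN023 ratio at the 1.25 limit (assumption).
- Lognormal AUEC0-t, log-scale SD s = √ln(1 + CV²).
- CV assumed at 20-50%. Protocol 7.7 uses 15-25% for RVNA at a time point and 10-20% for AUC; neither is stated for the area above 0.5 IU/mL.
- The k lowest SYN023 values are removed, and none from RIG.

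*Hand approximation.* In units of s, the three lowest of 80 normal values are expected at −2.427, −2.057 and −1.848. Removing k of them raises the SYN023 log mean by (sum of their absolute values)/(80 − k). The standard error is √(1/80 + 1/(80 − k)). False similarity is about Φ(−1.645 + shift/SE):
- k = 1: 2.427/79 = 0.0307; SE 0.1586; Φ(−1.645 + 0.194) = 7.3%
- k = 2: 4.484/78 = 0.0575; SE 0.1591; Φ(−1.645 + 0.361) = 10.0%
- k = 3: 6.332/77 = 0.0822; SE 0.1596; Φ(−1.645 + 0.515) = 12.9%

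Shift and SE both scale with s, so the CV hardly matters until it is large.

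*Simulation* (20,000 trials per cell, pooled-variance 90% interval within 0.80-1.25):

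| CV | k = 0 | k = 1 | k = 2 | k = 3 |
|---|---|---|---|---|
| 20% | 4.8% | 7.6% | 10.5% | 13.4% |
| 30% | 4.6% | 7.5% | 10.6% | 13.9% |
| 50% | 4.8% | 7.5% | 10.6% | 14.4% |
| 80% | 3.8% | 6.2% | 8.8% | 10.9% |

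The simulated values slightly exceed the hand values because trimming a tail also shrinks the pooled SD. If the analysis is run by vaccine (40 per arm, CV 25%), removing the 2 lowest gives about 13%.

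**The case against.** The plan has real safeguards, and several stronger readings fail against them.

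- *A reader might infer that nobody who shapes the primary data is blind.* That is wrong. The investigator, who shares the right to withdraw subjects, is blinded. So is the laboratory that produces the RVNA values. Protocol 3.6.5 has deviations categorized and documented as they occur.
- *A reader might infer that the analysis statistician is unblinded and that 3.4 cancels the safeguard in 3.3.* The documents do not show this. The natural reading is that 3.4 means the schedule statistician. What stands is that the analyst's status is unstated.
- *A reader might infer that the sponsor can steer the SAP with individual RVNA results from Day 42.* Protocol 7 requires the SAP to be final before database lock and before any unblinded preliminary review. Later changes must be documented. The Day 42 review may present individual data, but no recipient is named.
- *A reader might infer that interpolation touches the primary endpoint.* In SAP 10.3 it applies only to partial areas (AUEC0-7, 0-14, 14-t, 14-35).
- *A reader might infer that violations are judged case by case, or that the pharmacokineticist knows the arm when doing the PD work.* The documents are silent on how violations are judged, on when PK is run and on whether one person does both.

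It is also fair to say that this is an openly single-blind Phase 2 trial with an assayed endpoint and a mechanical trapezoidal area, and that the simulation assumes exactly the most damaging removals. All of this stands. None of it supplies a blinded step for per-protocol membership or for omitted areas. A final SAP that leaves major violations undefined does not settle them either.

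**Conclusion.** The concern holds as a gap in data selection for the per-protocol AUEC0-t test. The sponsor is expressly unblinded. The blinding of the analysis statistician and the pharmacokineticist is not stated. Two discretionary decisions need not be made blind or fixed before unblinding, and no all-dosed PD analysis is planned as a check.

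The figures of about 7.5%, 10.5% and 14% against 5% are a worst-case bound. They rest on a true ratio exactly at 1.25, 80 per group, an assumed CV of 20-50% and one-sided removal of the very lowest SYN023 values. They show how sensitive the test is to one to three exclusions. They do not predict that such exclusions would occur or suggest intent. This is a cheap improvement, worth making because the remedy is mostly wording.

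**What to change.** 1. **Protocol 3.4:** state that the unblinded statistician is the schedule statistician of 3.3, and that the analysis statistician stays blind until sign-off. Align 5.1.4 with this.
2. **SAP 6.2:** define major protocol violations and name who decides.
3. **SAP 6.2 and 10.3:** before unblinding, fix per-protocol membership and every non-calculated or interpolated PD parameter in a documented review held without arm or SYN023 concentrations. Those deciding must not hold treatment codes.
4. **SAP 12:** run the final PK analysis after that sign-off.
5. **SAP 10.4.1:** add an AUEC0-t sensitivity analysis on all dosed subjects, using the intent-to-treat population of Protocol 7.1.

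The schedule statistician should not be used to prepare the Day 42 tables, because 3.3 keeps that person out of the analysis.

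Cost: wording changes, one blind review step, one extra analysis and a slightly later start to the final PK work. No added subjects, visits or samples.

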### **3.4.1 Unblinding for Clinical Emergencies**

If there is an urgent clinical requirement to know a subject's treatment assignment, the investigator (in consultation with the medical monitor, if possible) will make a written request (handwritten is acceptable) to the Study Drug manager for urgent unblinding of a subject's treatment. The request must include the subject identification number, the date, a brief justification of the clinical requirement to the vaccine manager in the research pharmacy, and the investigator's signature. The request will be kept in the study file.

Upon receipt of proper written request, the vaccine manager or designee will disclose the treatment group to the investigator. The sponsor must be notified immediately of any clinically required break of the study blind on an Immediately Reportable Event Form.

### **3.5 Medicinal Product and Study Drug Administration**

There are four substances administered as part of this study. There are two study drugs SYN023 and rabies immune globulin (RIG): HyperRab ST® Grifols. SYN023 is investigational agent that has been administered previously to human subjects in a Phase 1 trial. RIG is licensed and

commercially available. SYN023 was tolerated acceptably in the initial human study thus enrollment of this study may be parallel between the different study groups. Vaccination will occur within 75 minutes after Study Drug administration. RVi, RVa, SYN023 and RIG will be administered by intramuscular injection. Generally antibodies should be administered on the right side of the body and vaccinations on the left side of the body to avoid administration in the same site.

### **3.5.1 SYN023 (Study Drug)**

One or more IM injections of the calculated dose of SYN023 should be administered in any of the acceptable injection sites on the RIGHT side of the body on Study Day 0. If for some reason left sided administrations sites must be used a record must be kept of the site and care taken to not administer SYN023 at a rabies vaccination site. SYN023 is supplied at a concentration of 10 mg/mL. For example a dose calculation for a 70 kg person receiving SYN023 at the dose of 0.3 mg/kg would require a dose of 21mg resulting in a dose volume of 2.1 mL. This would need to be administration into injection sites as described below. A needle no smaller than 21-gauge and 1.0 to 3.0 inches in length depending on subject size should be used to draw up the dose of SYN023. Aspiration of SYN023 from the vial should be done gently to avoid foaming.

SYN023 is to be administered as one or more IM injections in one of three possible injection site: the gluteus medius (ventrogluteal injection site/hip), the vastus lateralis (thigh), rectus femoris (thigh) and the deltoid muscle. Doses of up to 5 mL may be given as a single injection into the hip and thigh muscles. Doses up to 3 mL may be given if required in the deltoid muscle. No more than one injection may be administered into each muscle. Only a single deltoid administration is permitted in any subject. Injections into the gluteus maximus (buttocks) will not be performed.

When selecting the site of injection, known paths of nerves, arteries and veins are to be avoided. If available ultrasound assessment of thickness of fat pad and survey of nerve and blood vessel paths may be employed. The needle should be inserted into the skin at a 90° angle. Before SYN023 is administered, aspirate gently by pulling back on the plunger. If blood is drawn into the syringe, the needle is in a blood vessel and must be moved. Remove the needle from the muscle, re-insert it in a new location in the same muscle, and repeat the aspiration step before administering SYN023. If a dose of SYN023 is drawn up and cannot be administered immediately, the syringe may be stored at 2° to 8° C and used within 3 hours.

### **3.5.2 Rabies Immune Globulin, (HyperRab ST® Study Drug)**

RIG should be administered on the Right side of the body. If for some reason left sided administrations sites must be used a record must be kept of the site and care taken to not administer RIG at a rabies vaccination site. The dose of RIG should be calculated based on body weight: 0.133 mL/kg. The calculated dose should be administered as one or more IM injections in one of three possible injection sites: the gluteus medius (ventrogluteal injection site/hip), the vastus lateralis (thigh), rectus femoris (thigh) and the deltoid muscle. For example, a 70 kg person has a calculated dose of 9.31 mL. Since doses of up to 3 mL are recommended for the deltoid muscle, this will require dividing the dose between two injection sites. Doses of up to 5

mL may be given as a single injection into the hip and thigh muscles. Doses up to 3 mL may be given if required in the deltoid muscle. No more than one injection may be administered into each muscle. Only a single deltoid RIG administration is permitted in any subject. Injections into the gluteus maximus (buttocks) will not be performed.

When selecting the site of injection, known paths of nerves, arteries and veins are to be avoided. If available ultrasound assessment of thickness of fat pad and survey of nerve and blood vessel paths may be employed. The needle should be inserted into the skin at a 90° angle. Before RIG is administered, aspirate gently by pulling back on the plunger. RIG should not be administered intravenously. If blood is drawn into the syringe, the needle is in a blood vessel and must be moved. Remove the needle from the muscle, re-insert it in a new location in the same muscle, and repeat the aspiration step before administering RIG. RIG should be administered immediately, as soon as possible after the dose is constituted.

